5.2.2 Screen Failures/Dropouts

A subject who discontinues study participation prematurely for any reason is defined as a “dropout” if the subject has already been assigned to treatment and administered at least one dose of study drug.

A subject who, for any reason (e.g. failure to satisfy the selection criteria), terminates the study before the time point used for the definition of “dropout” (see above) is regarded a “screening failure”.

5.2.3 Replacement

Subjects/patients who discontinue from the study for reasons unrelated to the study (e.g., personal reasons or disease progression) will be replaced as required for the study to meet its objectives. The decision to remove a subject/patient and to replace dropouts will be made by the study investigator. Both the replacement and originally allocated number will be unique numbers.

6. Treatment

6.1 Treatments to be administered:

Monthly doses of Radium-223-dichloride

6.2 Treatment assignment

Patients will be screened with clinically appropriate tests for study inclusion. A patient number (a unique identification number from CORE in MD Anderson) will be assigned after a patient is evaluated for inclusion into the study and signs informed consent after successful screening.

6.2.1 Radium-223 dichloride

6.2.2 Treatments to be administered

Ra-223 dichloride will be administered as a slow bolus IV injection at intervals of every 4 weeks for up to 6 cycles.

- Dose (50, 75, or 100 kBq/kg) will be assigned in cohorts of 3 after study registration in CORE.
- Dose #1 should be given within 30 days of study registration
- At least 3 patients will be required to successfully complete 6 weeks of therapy before advancing to the next cohort.
- Patients will receive the same Ra-223-dichloride dose as dose #1 for all subsequent doses.
- Monthly dosing (q 4 weeks +/- 6 days) as slow iv bolus for up to a total of 6 doses
- Monthly doses will be delayed, but no more than 2 weeks from scheduled dose for any grade 3 hematologic toxicity.

Criteria for subsequent doses (i.e. doses 2-6):

- Hematologic Toxicity (if present): Hb, ANC, and platelets- resolved to grade 2 or less within 6 weeks of prior dose. Since lymphopenia may be chronic, this will not be a criteria for subsequent doses
- All toxicities must be resolved to grade 2 or less in order to begin subsequent cycles
- Performance status ECOG 0 to 2
- Alkaline phosphatase stable or improving at the discretion of the treating physician
- Not on oxygen
- Not pregnant
- After dose #3 and before dose #4: stable disease or better in indicator lesions as determined by quantitative nuclear medicine imaging (^{18}F FDG PET-CT, quantitative $^{99\text{m}}\text{Tc}$ -MDP SPECT/CT, or Na^{18}F PET/CT) or RECIST criteria on anatomic imaging (note: often osteosarcoma "indeterminate" lesions 1-9 mm remain stable or have minimal change depending on chest CT technique).
- Anatomic imaging (CT or MRI) of all sites of disease along with chest CT at baseline and restaging for all patients will be done to allow for assessment of RECIST progression.
- RECIST progression will determine progressive disease regardless of other imaging.

For the Phase I aspect of the protocol, prior to advancing/changing dose levels, a cohort summary must be completed and submitted to the Clinical Research Monitor in the IND Office.

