beforehand and given suitable personal protection equipment (i.e. universal blood and body fluid precautions - especially when handling ashes containing potentially radioactive bone fragments. Calculations and the rationale for radiation dose estimates are available upon request (see investigators Brochure).

Definition of Dose-Limiting Toxicities (DLTs):

Toxicities will be graded in severity according to the guidelines outlined in the NCI Common Terminology Criteria for Adverse Events (CTCAE) version 4.0 (publish date 28-May-2009). Dose-limiting toxicities include all adverse experiences that are related to study medication, and clearly not related to disease progression or intercurrent illness.

Based on prior experience with other bone seeking radiopharmaceuticals and Ra-223 dichloride in prostate cancer patients, the expected dose limiting toxicity (DLT) will be hematologic. Lymphopenia is common in patients with bone metastases and will be monitored, but not considered a DLT in this protocol. Any grade 4 anemia, any grade 4 neutropenia for >7 days or grade 4 neutropenia with fever (a single temperature greater than 38.3°C or a sustained temperature of $\geq 38^\circ\text{C}$ for more than one hour) and grade 3 or 4 thrombocytopenia with clinically significant bleeding will be dose limiting. Grade 3 non-hematologic toxicities except for nausea, emesis or diarrhea that are controlled with maximal medical management within 72 hours will be considered dose-limiting. DLTs will only be monitored during the first 6 weeks of treatment. Ongoing toxicity that causes a delay of more than 2 weeks in starting the next cycle will also be dose-limiting if it occurs during the first cycle.

Dose Modification and Escalation

Every effort should be made to administer the full dosing regimen of Ra-223 dichloride. Adjustment of dose level is not permitted.

- A minimum of 3 patients initially will be enrolled at the first dose level.
- If at least 2 patients are observed to have a dose-limiting toxicity (DLT), the MTD will have been exceeded and no further patients will be enrolled at this dose level or at any higher dose level. The prior dose level is defined as the MTD (unless only 3 patients have been treated at that level, in which case it is the tentative MTD).
- If 0 of the 3 patients are observed to have DLT during the DLT assessment period, the dose level is escalated one step for the next cohort of 3 patients, and the process continues as above.

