- If exactly 1 of the 3 patients treated show DLT during the DLT assessment period, 3 additional patients are treated at the current dose level.
- If none of these additional 3 patients show DLT during the DLT assessment period, the dose level is escalated for the next cohort of 3 patients, and the process continues as above; otherwise, the prior dose level is defined as the MTD (unless only 3 patients have been treated at that level, in which case it is the tentative MTD).
- A tentative MTD becomes final when a total of 6 patients are treated with less than 2 showing DLT.
- If 2 of the first 3 patients have hematologic DLT, then next cohort will be dose level -1.

Study visits during the treatment period should occur at 4 weeks intervals (within a window of +/- 7 days). **Dosing delays** may be instituted under the following circumstances:

Disease progression:

The Investigator should delay cytotoxic chemotherapy, other systemic radioisotope, hemibody external radiotherapy or other investigational drug until the follow-up period. If such treatments have to be given during the treatment period, further study drug administrations must be discontinued. Patients with disease progression may continue other treatment at the Investigator's discretion.

Myelosuppression:

Treatment-related changes in hematology parameters may occur.

- Blood transfusion is acceptable between study drug administrations. Use of biologic response modifiers, such as G-CSF or GM-CSF, is allowed in the management of acute toxicity.
- If myeloid growth factors are required for the management of acute toxicity this event should be considered a DLT.

Gastrointestinal events:

Diarrhea should be treated as per local practice. A further dose of study medication should not be given before diarrhea is recovered to CTCAE v4.03 Grade 2 or baseline levels.

Nausea or vomiting should be treated as per local practice. A further dose of study medication should not be given before nausea or vomiting is recovered to CTCAE v.4.03 Grade 2 or baseline levels.

For any grade 3 hematologic toxicity for >14 days, study drug administrations must be discontinued (grade 4 events of anemia and neutropenia >7 days are dose-limiting).

Spinal Cord Compression:

If the patient experiences spinal cord compression during the treatment period, the patient should be treated for the event, and this will be considered disease progression.

Surgical Intervention:

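### Where the 3+3 rule calls for 6 patients, the protocol does not require all 6 to be assessed for DLT before the level is cleared or the MTD is made final

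*Combined protocol and SAP*

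**What the plan says.** - **Gate for advancing (section 6.2.2):** "At least 3 patients will be required to successfully complete 6 weeks of therapy before advancing to the next cohort". This is the only completion requirement, and it is the same for every advance.
- **DLT window (Definition of Dose-Limiting Toxicities, under section 6.2.9):** "DLTs will only be monitored during the first 6 weeks of treatment".
- **First stage (Dose Modification and Escalation, under section 6.2.9):** the dose goes up one step on this condition: "If 0 of the 3 patients are observed to have DLT during the DLT assessment period". After exactly 1 DLT in 3, "3 additional patients are treated at the current dose level".
- **Second stage (same list):** "If none of these additional 3 patients show DLT during the DLT assessment period, the dose level is escalated".
- **MTD (same list):** "A tentative MTD becomes final when a total of 6 patients are treated with less than 2 showing DLT".
- **Replacement (section 5.2.3):** patients who leave for reasons such as personal choice or progression are to be replaced as far as the study's objectives need it. Then: "The decision to remove a subject/patient and to replace dropouts will be made by the study investigator".
- **Analysis sets:** section 8.1 carries that heading but defines no set. Section 7.4 gives a safety set of everyone who received at least one dose. No DLT-evaluable population is defined.

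**The concern.** A 3+3 rule has its usual properties only if each patient it counts has either been followed through the DLT window or had a DLT. Here the completion floor does not rise with the number of patients the rule calls for. After 1 DLT in the first 3, two patients have completed, so one further completer among the 3 added satisfies section 6.2.2. The other two could leave inside 6 weeks and still, literally, show no DLT. The MTD rule is looser still. The gate governs only advancing, so the text does not require any of the second 3 to be observed for 6 weeks.

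Later safety reporting would not reliably fill the gap. Section 5.2.1 ends treatment and procedures on progression. SAE capture runs to 30 days after the last dose (section 7.4.1.2.1), which is 12 days short of the 42-day window for a patient given one dose. An isolated grade 4 laboratory value is not reportable as an SAE unless the investigator judges that it meets the standard criteria (section 7.4.1.4), yet the protocol expects DLTs to be hematologic.

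The MTD or recommended dose is the primary objective. Any error from this source runs one way, toward clearing or confirming a level that is too toxic, and the 6 expansion patients are then treated at the chosen dose.

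**Working it through.** **The plan's own figures.** The protocol gives no operating characteristics, target DLT rate or dropout rate for the 3+3 rule, so there is nothing of that kind to reproduce. Its sample size reproduces from Table 1: 3 + 3 + 8 + 6 = 20. Section 8.5 counts 9 + 6 = 15, which is a separate inconsistency and does not affect this point.

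**Inputs.** From the protocol: 3 then 3 more patients, a 6-week window, a floor of 3 completers, and fewer than 2 DLTs in 6. Assumed: true DLT rate *p* = 0.33, 0.40 or 0.50. Also assumed: each patient in the second 3 leaves early with probability *d* = 0.1, 0.2 or 0.3, with no DLT seen, is not replaced, and is counted as having shown none. The first 3 are fully followed.

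**Clearing a level.**
P(clear) = (1−p)³ + 3p(1−p)² × S, where S is the chance that the second 3 show no DLT.
- All 3 followed: S = (1−p)³.
- Early loss *d*, gate kept: S = (1−p(1−d))³ − d³ + d³(1−p). The last two terms apply the gate: if all 3 leave, one more patient must complete.
- Gate minimum, one added patient followed: S = 1−p.

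At p = 0.40, (1−p)³ = 0.216 and 3p(1−p)² = 0.432.
- All followed: 0.216 + 0.432 × 0.216 = 0.309.
- d = 0.2: S = 0.68³ − 0.008 + 0.0048 = 0.311, so 0.216 + 0.432 × 0.311 = 0.350.
- Gate minimum: 0.216 + 0.432 × 0.6 = 0.475.

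| p | All 6 followed | d = 0.1 | d = 0.2 | d = 0.3 | Gate minimum |
|---|---|---|---|---|---|
| 0.33 | 43.4% | 45.5% | 47.7% | 49.9% | 59.9% |
| 0.40 | 30.9% | 32.9% | 35.0% | 37.3% | 47.5% |
| 0.50 | 17.2% | 18.7% | 20.4% | 22.3% | 31.2% |

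For d = 0.1 to 0.3 the increase runs from 1.5 points (p = 0.50, d = 0.1) to 6.5 points (p = 0.33, d = 0.3).

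**Fewer than 2 DLTs among 6 treated.** With r = p(1−d) for the second 3:
P(confirm) = (1−p)³ × [(1−r)³ + 3r(1−r)²] + 3p(1−p)² × (1−r)³.
At p = 0.40 and d = 0.2, r = 0.32: 0.216 × (0.314 + 0.444) + 0.432 × 0.314 = 0.300.

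| p | All 6 followed | d = 0.1 | d = 0.2 | d = 0.3 | None of second 3 followed |
|---|---|---|---|---|---|
| 0.33 | 35.8% | 39.1% | 42.6% | 46.2% | 74.5% |
| 0.40 | 23.3% | 26.5% | 30.0% | 33.6% | 64.8% |
| 0.50 | 10.9% | 13.4% | 16.2% | 19.3% | 50.0% |

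The increase for d = 0.1 to 0.3 runs from about 2.5 to about 10 points. These figures take the level from its first patient. For a tentative MTD that already stands at 0 of 3, only the bracket applies. At p = 0.40 it is 64.8% with full follow-up and 75.8% at d = 0.2. Multiplied by the 21.6% chance of 0 of 3, that is 14.0% and 16.4%.

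**With replacement.** If every early leaver is replaced by a patient who is followed, d = 0 and both tables return to their first column.

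**The 0 of 3 route.** Advancing after 0 of 3 needs 3 completers under section 6.2.2, so all of the first 3 must have been followed. There is no gap on that route.

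**The case against.** The strongest reply is that the second-stage bullet speaks of the 3 added patients during the DLT assessment period, and its natural reading is that all three go through that period. On that view the floor of 3 in section 6.2.2 works alongside the rule and does not replace it. Section 5.2.3 foresees replacement for the two likeliest reasons for leaving, and with replacement there is no inflation. Scheduled restaging comes after dose 3 of a 4-weekly regimen, so progression found at a scheduled scan falls outside the 6-week window. Blood counts are taken every 2 weeks in the first two cycles, so a patient who leaves late in the window has been largely observed. A cohort summary goes to the IND Office before any change of dose level, and section 8.1 halts accrual for review if more than two expansion patients have DLTs.

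Most of this stands, and it limits the size of the problem. It does not remove it. Replacement is conditional and discretionary, with no criterion linked to the window. The protocol does not say that the cohort summary must check evaluability. The expansion review comes after the MTD has been chosen. Whether a patient with a DLT can have successfully completed 6 weeks is also unstated. Section 5.2.1 lists DLT among the reasons for mandatory withdrawal, which suggests not. If such a patient did count, the floor would already be met before any added patient was followed.

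A reader might infer that the protocol counts early dropouts as DLT-free. It does not say so: it is silent, and the wording merely permits that count. A reader might also infer that early loss is likely. The documents give no rate of early loss.

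**Conclusion.** The point holds for 6-patient levels. The protocol does not require all 6 to be assessed, defines no DLT-evaluable population, and does not tie replacement to the 6-week window. A level could be cleared on 4 assessed patients, or a tentative MTD made final with none of the second 3 observed through the window, without breaking a stated rule.

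The likely size is modest. At a true DLT rate of 40%, clearance rises from 30.9% to between 32.9% and 37.3% for 10-30% unreplaced early loss. Confirmation on 6 treated rises from 23.3% to between 26.5% and 33.6%. The DLT rates and loss rates are assumptions. The model also gives each early leaver no chance of a recorded DLT, which overstates the effect for those who leave late in the window.

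It would be tempting to quote 47.5% for clearance, or certainty of confirmation after 0 of 3, as the protocol's error rate. Neither is supported. Both need at least two of the 3 added patients to be lost and not replaced, which at 20% loss has probability 3 × 0.2² × 0.8 + 0.2³ = 10.4%.

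This should be fixed, because the rule decides the primary outcome and the repair is small. The documents do not show that the design is unsafe as it would normally be run.

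**What to change.** 1. **Section 6.2.2.** Replace the 3-completer bullet with wording such as: *A dose level is escalated, or an MTD made final, only when every patient the rule counts (3, or 6 where the level has been expanded or a tentative MTD is being confirmed) has completed the 6-week DLT window or had a DLT. The stop on 2 or more DLTs applies as soon as the second DLT occurs.* The condition must be limited to decisions to escalate or finalise. If it covered every decision, it would delay the existing stop.
2. **Dose Modification and Escalation.** Define DLT-evaluable as having completed the window or had a DLT. Use that term for the 3 added patients in the second-stage bullet, and in place of *treated* in the tentative-MTD bullet.
3. **Section 5.2.3.** Make replacement of a non-evaluable patient mandatory before either decision. Keep the replaced patient in the safety set.

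The cost is a few sentences, an occasional replacement patient of the kind section 5.2.3 already foresees, and a few weeks' wait when one is needed. No dose or DLT criterion changes. Clearance and confirmation then return to the ordinary 3+3 values in the first column of each table.

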6.2.3 Identity of study treatment

The alpha-pharmaceutical Ra-223 dichloride is a ready-to-use, sterile, non-pyrogenic, clear and colorless aqueous solution of Ra-223 dichloride for IV administration. Ra-223 dichloride is an alpha particle emitter with a physical half-life of 11.4 days. The product is isotonic and has a pH of 6.0-8.0. The radioactive concentration at the reference date is 1000 kBq/mL. The product has a pre-calibration of 14 days. When administered on a day other than the reference day, the volume should be corrected according to the physical decay table.

Bayer Corporation will provide Ra-223 dichloride, which will be manufactured by the contract manufacturer: Institute for Energy Technology, Isotope laboratories, Kjeller, Norway. The product is produced according to Good Manufacturing Practice (GMP). The product will be delivered in a glass vial, ready-to-use with a certified activity. Ra-223 dichloride is shipped in a lead container and Type A radioactive package according to international transportation guidelines for radioactive materials.

The volume per vial is 6 mL, corresponding to 6 MBq at the calibration day. Ra-223 dichloride has a shelf life of 28 days from production day, when stored at ambient temperature. The shelf life has been demonstrated for temperatures from cold storage (2-8°C) up to 40°C. In addition, it has been shown that the product quality is not jeopardized upon freezing.

All study drugs will be labeled according to the requirements of local law and legislation. For all study drugs, a system of numbering in accordance with all requirements of GMP will be used, ensuring that each dose of study drug can be traced back to the respective bulkware of the ingredients.

6.2.4 Dosage and administration

Written information about Ra-223 dichloride and instruction about handling and injection of radioactive material will be provided to study personnel.

In general, the administration of radioactive drugs involves a potential risk for third parties, due to radiation from the patient and due to possible contamination by spilling urine or feces. When Ra-223 dichloride has been injected intravenously into a patient, the risk for external radiation exposure to third parties is extremely low, due to the short range of the alpha particles (<100 µm) and the low portion of beta and gamma radiation. For these

reasons the product can be administered on an out-patient basis. To minimize the risk of contamination, the patient and his caregivers will receive oral and written instructions regarding hygiene precautions to abide by after receiving the radioactive drug.

6.2.5 Dose calibration

Ra-223 dichloride can be measured in a normal dose calibrator instrument. When written approvals for the use of Ra-223 dichloride from the Radiation Protection Agency for the specific center have been received by the sponsor, a vial of Ra-223 dichloride for technical use will be sent to the study center.

Different clinical study centers possess dose calibrators from various suppliers; thus, the isotope calibration factor may differ from center to center. Consequently, each center must perform the Ra-223 dichloride dial setting on their relevant dose calibrator(s). For dial setting, the clinical study center will receive a sealed vial containing a Ra-223 dichloride solution for calibration only. The vial is identical to the vials used for study treatment. The amount of Ra-223 dichloride in the vial will be stated on the label. Instructions for the dial setting, including the calibration log form, will be enclosed with the dispatch of the calibration sample.

6.2.6 Dose handling

The Ra-223 dichloride vials must be stored inside their lead container in a secure facility. The study drug should be used within 28 days of production. Ra-223 dichloride is an alpha-pharmaceutical and should be handled by individuals who are qualified by training and experience in the safe handling of radionuclides. One dedicated person and a back-up designee will have responsibility as assigned from the Primary Investigator for handling and storage of Ra-223 dichloride. Control measurements of both the Ra-223 dichloride vial (before and after dispensing) and syringes (before and after administration) are performed as part of the clinical trial documentation. All administrations of Ra-223 dichloride are based on the certified activity of Ra-223 dichloride at the calibration date.

6.2.7 Dose calculation

The dosage of Ra-223 dichloride is 50, 75, or 100 kBq/kg body weight. The total activity to be injected will be calculated volumetrically using the patient's body weight on the day of injection (kg), the 50 kBq/kg body weight dosage level, and the decay correction factor (DK) to correct for physical decay of Ra-223 dichloride. A table with DKs according to physical decay of the study medication will be provided with each vial of Ra-223 dichloride. The total amount (volume to be drawn into the syringe) to be administered to a patient should be calculated as follows:

$\text{Body weight (kg)} \times 50 \text{ kBq/kg} = \text{volume to be injected (mL)}$
 $\text{DK} \times 1000 \text{ kBq/mL}$

Data regarding activity should be recorded on the appropriate electronic case report form (eCRF) page.

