The goal of this initial study is to determine the safety of escalating doses of monthly Ra-223 dichloride in osteosarcoma patients with osteoblastic bone-forming metastases until MTD or a dose 100 kBq/kg dose is reached (whichever is first). Radium-223 dichloride will be given monthly for up to 6 cycles and side effects of this bone-targeted therapy on monthly blood counts and alkaline phosphatase will be determined. After 3 and 6 doses patients will have imaging to compare ^{99m}TcMDP uptake to baseline and other imaging as clinically indicated including ¹⁸F-FDG PET-CT, Na¹⁸F and/ chest CT. Anatomic imaging (CT or MRI) of all sites of disease along with chest CT at baseline and restaging for all patients will be done to allow for assessment of RECIST progression. RECIST progression will determine progressive disease regardless of other imaging.

Table 1. Ra-223 dichloride Dose Escalation scheme (N=3/cohort)

Dose level:	kBq/kg	N
-1	25	--
0 (starting dose)	50	3
1	75	3
2	100	8
Expansion cohort	MTD	6

Anticipated Total N = 9- 20 (N= 20 assumes reaching 100 mBq/kg MTD)

***Imaging:** Three modalities will be compared
pre vs after dose 3 and after dose 6
ΔSUV of ¹⁸F PET-CT
ΔSUV Na¹⁸F PET-CT
Δ activity ^{99m}Tc-MDP SPECT -CT

Table 2. Decay and Marrow/Bone Ratios Clinically Useful Bone-seeking Isotopes

	Half-life	*Ratio of Surface	Particle	MeV particle	Range
	Days	Bone : red marrow		Emission energy	(mm)
¹⁵³ Sm-EDTMP	2	4.4	Beta	0.66 max 0.22 average	0.6
⁸⁹ SrCl ₂	50.5	1.6	Beta	0.58	2.4
²²³ RaCl	11.4	10.3	Alpha	27.4	<0.1

* Bone surface to red bone marrow radioactivity dose ratio

Table 3. Comparison of Alpha and Beta Particles from Bone-Seeking Cancer Drugs

Characteristic	Alpha	Beta
Range (um)	40-90	50-6000
Linear Energy Transfer*	60-230	0.015-0.4

Relative mass	7000**	1**
DNA hits to kill a cell	1-5	100-3000
Cytotoxic against G ₀ cells	Yes	No
Effective against “radio-resistant” cells	Yes	No

*(LET; keV/μm)

**Alpha particles are dense particles (i.e. like a helium nucleus); beta particles are electrons

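### The only injection-volume formula (Section 6.2.7) fixes the dose at 50 kBq/kg for every cohort, which is wrong at every dose level except 50

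*Combined protocol and SAP*

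**What the plan says.** Section 6.2.7 (Dose calculation) opens with: "The dosage of Ra-223 dichloride is 50, 75, or 100 kBq/kg body weight". Its next sentence calculates the activity to inject from the day's body weight, "the 50 kBq/kg body weight dosage level, and the decay correction factor (DK"). The displayed formula repeats that constant: body weight × 50 kBq/kg over DK × 1000 kBq/mL gives the volume in mL.

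Elsewhere the dose depends on the cohort:

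- Section 6.2.2: "Dose (50, 75, or 100 kBq/kg) will be assigned in cohorts of 3 after study registration in CORE". It also keeps each patient on the dose-1 level for all later doses.
- Section 4, Table 1 ("Ra-223 dichloride Dose Escalation scheme (N=3/cohort"): level -1 is 25, level 0 is 50, level 1 is 75 and level 2 is 100 kBq/kg.
- Dose Modification and Escalation (after Section 6.2.9): "If 2 of the first 3 patients have hematologic DLT, then next cohort will be dose level -1".

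On checking what was given, Section 6.2.6 requires vial and syringe measurements as trial documentation and states: "All administrations of Ra-223 dichloride are based on the certified activity of Ra-223 dichloride at the calibration date". Section 6.2.7 adds: "Data regarding activity should be recorded on the appropriate electronic case report form (eCRF) page". Section 6.2.2 requires that "prior to advancing/changing dose levels, a cohort summary must be completed and submitted to the Clinical Research Monitor in the IND Office", and Section 9.2 calls for data review at each dose level.

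**The concern.** The section contradicts itself and the cohort assignment in Section 6.2.2. The 50 appears in both the prose and the formula, so it is not a PDF-reading error. Section 6.2.3 says only that the volume is corrected for decay, and Section 6.2.8 tells the preparer to draw the correct volume without defining it. Section 6.2.7 is therefore the only place where that volume is defined, and nothing there tells staff to substitute the assigned level.

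The primary objective (Synopsis; Section 2.1) is to find the maximum tolerated or recommended dose and to compare safety at 50, 75 and 100 kBq/kg. If the formula were applied as printed and the error were missed, three things would follow:

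- Cohorts labelled 75 and 100 would receive 50. Escalation and the six-patient expansion would rest on those labels, and 100 kBq/kg could be declared tolerable without any patient having received it.
- If the 50 kBq/kg start proved too toxic, that finding would remain valid, because the formula is right at 50.
- In that same event, however, the de-escalated cohort would receive twice its assigned dose: the same 50 kBq/kg that had just caused the dose-limiting toxicities.

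**Working it through.** **Inputs from the protocol**

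- Constant in the formula: 50 kBq/kg (Section 6.2.7).
- Product concentration at the reference date: 1000 kBq/mL (Section 6.2.3).
- Assigned levels: 25 (level -1), 50, 75 and 100 kBq/kg (Table 1).
- Entry weight: above 40 kg (Section 5.1.1).

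The plan states no numerical volume, so there is none to reproduce.

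**Dose delivered by the printed formula**

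Volume = weight × 50 / (DK × 1000).

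Delivered kBq/kg = volume × DK × 1000 / weight = 50, for any weight and any DK.

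Delivered/assigned = 50 / assigned level.

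**Volumes for illustration.** I assume DK = 1 and weights of 70 kg and 40 kg (the latter at the entry limit). The correct volume is weight × assigned level / 1000.

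| Assigned kBq/kg | Delivered/assigned | 70 kg: formula vs correct (mL) | 40 kg: formula vs correct (mL) |
|---|---|---|---|
| 25 (level -1) | 50/25 = 200% | 3.5 vs 1.75 | 2.0 vs 1.0 |
| 50 | 50/50 = 100% | 3.5 vs 3.5 | 2.0 vs 2.0 |
| 75 | 50/75 = 67% | 3.5 vs 5.25 | 2.0 vs 3.0 |
| 100 | 50/100 = 50% | 3.5 vs 7.0 | 2.0 vs 4.0 |

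A different DK scales both volumes equally and leaves the percentages unchanged.

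**Level -1.** The 200% uses Table 1's 25 kBq/kg. The Synopsis also uses the label dose -1 for 50 kBq/kg, but there it means one step below 75 after 2 of 3 patients have a DLT at 75. Table 1 is the right source when the starting dose itself is too toxic. The dosage list in Section 6.2.7 omits 25 kBq/kg.

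**Would the existing checks catch it?** A syringe filled by the formula would contain the activity the formula predicts, so a measurement made only for documentation would agree with it. The eCRF entry, the cohort summary and the review at each dose level could each reveal the error, but the protocol does not state that activity is compared with the assigned kBq/kg at any of these steps.

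**The case against.** The strongest reply is that literal misuse is unlikely. The three doses head the same section, and Section 6.2.2 ties the dose to the cohort. Section 6.2.6 restricts handling to people qualified by training and experience. Sections 6.2.4 and 6.2.9 promise written instructions to staff, which are not in the document and may give the calculation by cohort. The cohort-summary form and eCRF pages are not available either, so a comparison with the assigned dose may exist there. Level -1 has no planned patients in Table 1, so the 200% case needs both a toxicity contingency and literal use of the formula.

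These points stand as arguments about probability. Competent staff may well substitute the right level, and the protocol's silence about a comparison does not prove that none is made. But none of this corrects the text. Section 11.1 demands strict adherence to every specification in the protocol. At 75 or 100, staff must therefore depart either from the printed formula or from the cohort assignment.

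**Conclusion.** The concern holds. Section 6.2.7 is wrong as written: its formula gives the assigned dose only at 50 kBq/kg, and otherwise 67% at 75, 50% at 100 and 200% at level -1. The percentages follow from the printed constant and Table 1 and need no assumption about weight or decay; only the example volumes do.

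Confidence is high that the error exists. How likely it is to reach a patient cannot be judged from the document, and nothing there indicates that it did. It must still be fixed, because it is the sole written dosing formula in a trial whose primary question is dose, and it bears directly on patient safety.

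**What to change.** In Section 6.2.7, replace 50 kBq/kg in both the calculation sentence and the formula with the patient's assigned dose level: 50, 75 or 100 kBq/kg, or 25 kBq/kg if level -1 is opened. The formula becomes: volume = weight × assigned level / (DK × 1000).

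As an optional safeguard, add to the cohort summary required by Section 6.2.2 a comparison, for each dose given, of the activity recorded on the eCRF with the assigned kBq/kg.

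The cost is a one-line correction, plus one comparison using data already collected if the safeguard is adopted. Design and sample size are unchanged, and the fix takes no view on which dose is right.
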